### 8.3 TIME PERIOD AND FREQUENCY FOR EVENT ASSESSMENT AND FOLLOW-UP

The occurrence of an AE or SAE may come to the attention of study personnel during study sessions. All AEs including local and systemic reactions 1) not meeting the criteria for SAEs, 2) not included in the list of expected events in Section 8.2.3, or 3) beyond a threshold for an expected event listed in Section 8.2.3 (such as greater than mild symptoms or significant change from baseline in pain, anxiety, drowsiness, or nausea) will be captured on the appropriate case report form by a CUChange Lab professional research assistant. Information to be collected includes event description, time of onset, assessment of severity, and time of resolution/ stabilization of the event.

[figure not shown]
Changes in the severity of an AE will be documented to allow an assessment of the duration of the event at each level of severity to be performed. AEs characterized as intermittent require documentation of onset and duration of each episode.

At each study visit, the professional research assistant will inquire about the occurrence of AE/ SAEs since the last visit.

### 8.4 REPORTING PROCEDURES

#### 8.4.1 ADVERSE EVENT REPORTING

[figure not shown]
The study team will adhere to the protocol detailed in the figure below for reporting adverse events.

The study team will record all reportable events with start dates occurring any time after informed consent is obtained until seven days after the last day of study participation. All AEs will otherwise be followed to adequate resolution or stabilization.

#### 8.4.2 SERIOUS ADVERSE EVENT REPORTING

Since the study procedures are not greater than minimal risk, SAEs are not expected. Should an SAE occur, the study team will adhere to the protocol detailed in the figure below for reporting serious adverse events.

The study team will record all reportable events with start dates occurring any time after informed consent is obtained until 30 days after the last day of study participation. All SAEs will otherwise be followed to adequate resolution or stabilization.

#### 8.4.3 UNANTICIPATED PROBLEM REPORTING

Since the study procedures are not greater than minimal risk, UAPs are not anticipated. Incidents or events that meet the OHRP criteria for UAPs require the creation and completion of a UAP report form and including the following information:

- Protocol-identifying information: protocol title and number, PI's name, and the IRB project number;
- A detailed description of the event, incident, experience, or outcome;
- An explanation of the basis for determining that the event, incident, experience, or outcome represents a UAP;

- A description of any changes to the protocol or other corrective actions that have been taken or are proposed in response to the UAP.

To satisfy the requirement for prompt reporting, UAPs will be reported using the following timeline:

- UAPs that are SAEs will be reported to the IRB within 24 hours of the investigator becoming aware of the event.
- Any other UAP will be reported to the IRB within 72 hours of the investigator becoming aware of the problem.

#### **8.4.4 REPORTING OF PREGNANCY**

Patients who are pregnant or trying to become pregnant are ineligible for participation. If a participant becomes pregnant after enrolling in the study, the participant will be withdrawn.

### **9 CLINICAL MONITORING**

Clinical site monitoring will be conducted to ensure that the rights and well-being of human participants are protected, that the reported trial data are accurate, complete, and verifiable, and that the conduct of the trial is in compliance with the currently approved protocol/ amendment(s), with GCP, and with applicable regulatory requirement(s).

Monitoring for this study will be performed by CU Cancer Center Clinical Monitor in accordance with the clinical monitoring plan (CMP), incorporated herein by reference. The CMP describes in detail who will conduct the monitoring, at what frequency monitoring will be done, at what level of detail monitoring will be performed, and the distribution of the monitoring reports.

The principal investigator will be responsible for the conduct of this study, overseeing participant safety, executing the data and safety monitoring (DSM) plan, and complying with all reporting requirements to local and federal authorities. This oversight will be accomplished through additional oversight from the Data and Safety Monitoring Committee (DSMC) at the University of Colorado Cancer Center (CU Cancer Center). The DSMC is responsible for ensuring data quality and study participant safety for all trials at the CU Cancer Center. A summary of the DSMC's relevant activities is as follows:

- Conduct of internal audits
- May submit recommendations for corrective actions to the CU Cancer Center's Executive Committee

Study audits conducted by the DSMC will consist of a review of the regulatory documents, consent forms, and source data verification. Documentation of the audit conducted by the DSMC will then need to be submitted to the IRB of record at the time of the IRB's continuing review of this trial (if applicable).

## 10 STATISTICAL CONSIDERATIONS

### 10.1 STATISTICAL AND ANALYTICAL PLANS

This is a feasibility study and thus underpowered for meaningful analysis; the endpoints are strictly recruitment based. We will however examine the data for completeness (i.e., were any measures or items consistently left blank). In addition, we will examine the summary statistics including mean and standard deviation for continuous items as well as skew and kurtosis to evaluate whether the measures approximate a normal distribution. For categorical outcomes, we will examine proportions in each category to get some idea of variability on the measure.

### 10.2 STATISTICAL HYPOTHESES

- Primary Efficacy Endpoint(s):  
This section is not applicable.
- Secondary Efficacy Endpoint(s):  
This section is not applicable.

### 10.3 DESCRIPTION OF STATISTICAL METHODS

#### 10.3.1 ADHERENCE AND RETENTION ANALYSES

This feasibility study has an 80% retention goal for reasonable compliance with study procedures by enrolled study participants. Reasonable compliance is defined as 75% completion of study assessments. Adherence is not applicable to this observational study design.

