**Endpoint:**

  - ***Recruitment Outcomes:***  
Number of interested patients who contact the research team  
Number of eligible potential participants  
Number of enrolled eligible participants  
Number of study assessments completed by enrolled participants  
Number of participants who complete the study

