by current cancer patients. Specifically, we wish to determine whether it is feasible to appraise the effects of orally administered *Cannabis* products among a cancer patient group by determining whether this group is willing to participate in all necessary components of a study examining how differing ratios of cannabinoids in cannabis products (based on type of product strain used) relate to symptom relief, quality of life, and cognitive measures.

**2.1.2. Psychological effects of *Cannabis* use in cancer patients.** There is some research that suggests the potential for positive psychological effects of *Cannabis* use that may improve quality of life. For example, some of the effects that are commonly described as adverse or harmful (e.g., feeling “high”, euphoria, sleepiness), may be reframed as positive effects for those suffering from cancer and the side effects of treatment (i.e., mood elevation, reduced anxiety, improved sleep quality). One study examined the effects of medical *Cannabis* on psychological symptom management by interviewing Israeli cancer patients before and 6-8 weeks after they received a medical *Cannabis* license, and found reductions in self-reported mood disorders, sleep disorders, and pain, as well as reduced use of pain medication and depression/anxiety medication after initiation of medical *Cannabis* use. Given these findings, the study authors concluded that medical *Cannabis* may be an important contribution to palliative cancer care.

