### 4.1 DESCRIPTION OF THE STUDY DESIGN

Tightly controlled experimental laboratory studies (e.g., clinical trials with randomization) using *Cannabis* products available in state-regulated markets are simply, at this point, not possible owing largely to federal law and the University requirements related to the Controlled Substances Act and Drug Free Schools and Communities Act. Because a traditional clinical trial design is not possible given the current federal status of *Cannabis* products, we will use a patient-oriented, prospective observational design. Specifically, individuals who have already decided to try *Cannabis* for their cancer treatment-related symptoms will initiate use of an orally administered product they have selected. A research assistant will provide information on the range of edible cannabis products and basic information about their various cannabinoid profiles, approximate prices, and nearby locations where participants may choose to purchase their product. The participants will then purchase the product and decide how often and how much to use. This approach is consistent with federal law and supported by our preliminary and ongoing studies (1R01AT009541-01, 1R01DA044131-01, CDPHE2902, R01DA039707). Participants will take the product as they see fit, without any frequency or dosing instructions from study staff, for two weeks, at which time they will be scheduled for their Pre- and Post- Administration Assessment (Ta1-Tc1) so that we may examine the acute effects of the product. The final follow-up will be one month later via an online survey sent directly to the participant via email. Details about the various study sessions are provided in Section 7.

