#### **6.1.3 DOSING AND ADMINISTRATION**

The patient will use their orally administered *Cannabis ad libitum* at home. This aspect of the design is again consistent with an observational design and differentiates it from a classical interventional clinical trial, which is critically important because it is the only path forward for research on orally administered, legal market *Cannabis* given current federal law. Study staff will not advise participants on or participate in dosing and administration practices.

The disadvantage of our observational design is that we do not have direct control over the choice of product or the dosing and administration of the *Cannabis* product. To address this limitation, we will have participants take and send a picture of their purchased oral cannabis product to our lab via the REDCap system. Colorado requires all strains to be tested by a state licensed lab, and the dispensary that we work with performs cannabinoid and terpene potency testing on each batch produced and sets aside a specific lot of strains corresponding to the ratios utilized in this project (a CBD-dominant strain, a THC-dominant strain, and a THC+CBD strain). Thus, having a picture of the participant's purchased product will allow us to verify the strain and thus, the ratio of cannabinoids contained in the product for a measure of potency to operationalize our user groups.

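### The compliance rule in section 10.3.1 requires no product purchase, photo or use and leaves the assessment unit undefined, so a participant who never takes an oral product can count as compliant

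*Combined protocol and SAP*

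**What the plan says.** Section 2.1.1 gives the purpose: to learn whether cancer patients are "willing to participate in all necessary components of a study examining how differing ratios of cannabinoids in cannabis products" relate to symptoms, quality of life and cognition. Sections 3 and the synopsis state the objective as enrolling 30 patients with reasonable compliance with study procedures.

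Section 10.3.1 makes this operational in three sentences. The cohort target is: "This feasibility study has an 80% retention goal for reasonable compliance with study procedures by enrolled study participants". The participant-level threshold and the sentence on adherence follow: "Reasonable compliance is defined as 75% completion of study assessments. Adherence is not applicable to this observational study design". The unit of an assessment (item, instrument, time point or session) is not given.

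The synopsis endpoints are counts of contacts, eligible patients, enrolled patients, completers, and "Number of study assessments completed by enrolled participants".

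The steps particular to this design appear elsewhere. Entry needs only intent to use (section 5.1). The participant then buys a product and sends a photo; under section 6.1.3, "having a picture of the participant's purchased product will allow us to verify the strain", and this is how the user groups are to be formed. After two weeks comes one appointment made up of Ta1, an intake, Tb1 at one hour and Tc1 at two hours (section 7.3.3). Section 4.1 says it is scheduled "so that we may examine the acute effects of the product".

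**The concern.** The larger study would relate the cannabinoid content of a chosen product to outcomes, including acute outcomes measured after an intake. It can run only if patients buy an identifiable oral product, take it, and complete the post-dose tests. These are the steps whose feasibility is least certain in this population, and the compliance rule asks for none of them.

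Tb1 and Tc1 are also short blocks, so in a count of measures they carry little weight beside T00, Ta1 and M1. They come last in a 2.5-hour appointment, and section 5.3.4 itself warns that assessments may be too taxing and that patients may wish to quit.

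At stake is the feasibility answer. The study could report that its compliance goal was met when the exposure or the post-dose measurements did not take place in some of the participants counted as compliant. Because the unit is undefined, the same participant can pass or fail according to a counting choice made after the data are seen.

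**Working it through.** **Plan's own figures.** The 75% and 80% thresholds are set, not derived, so there is no formula to reproduce. For 30 enrolled, the cohort goal is 0.80 × 30 = 24 participants. The Table 7.1 totals agree with their parts: 90 + 150 + 20 = 260 minutes = 4 h 20 min, and $60 + $100 + $10 = $170.

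**Inputs.** Marks per row of Table 7.3 (14 columns); instruments named in its key; measures listed per time point in Table 7.1; the five time points; the three appointments in section 5.3.4.

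**Formula.** Completion = (total scheduled − missed) / total scheduled, compared with 0.75.

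| Unit | T00 | Ta1 | Tb1 | Tc1 | M1 | Total | Tb1 and Tc1 missed | Ta1, Tb1 and Tc1 missed |
|---|---|---|---|---|---|---|---|---|
| Table 7.3 marks | 13 | 11 | 5 | 5 | 12 | 46 | 36/46 = 78.3% | 25/46 = 54.3% |
| Same, without AE and EMR | 11 | 10 | 4 | 4 | 10 | 39 | 31/39 = 79.5% | 21/39 = 53.8% |
| Instruments, without AE and EMR | 15 | 14 | 6 | 6 | 14 | 55 | 43/55 = 78.2% | 29/55 = 52.7% |
| Table 7.1 measures | 11 | 9 | 3 | 3 | 9 | 35 | 29/35 = 82.9% | 20/35 = 57.1% |
| Same, without EMR | 10 | 9 | 3 | 3 | 8 | 33 | 27/33 = 81.8% | 18/33 = 54.5% |
| Time points | 1 | 1 | 1 | 1 | 1 | 5 | 3/5 = 60% | 2/5 = 40% |
| Whole sessions | 1 | one joint session | | | 1 | 3 | 2/3 = 66.7% | 2/3 = 66.7% |

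By minutes, losing the whole two-week appointment leaves (260 − 150)/260 = 42.3%. Table 7.1 does not split the 150 minutes, so no figure by minutes can be given for Tb1 and Tc1 alone.

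**Route 1, forms without an intake.** The rule counts assessments only. If every scheduled form is completed and nothing is taken, the numerator equals the denominator: 100% on any unit. This assumes that staff open the Tb1 and Tc1 forms although section 7.3.3 times them from consumption. If they do not, the case becomes route 2.

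**Route 2, both post-dose blocks missed.** This passes on all five cell, instrument and measure counts (78.2% to 82.9%) and fails by time points and by sessions.

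**Room left in route 2.** With Table 7.3 marks, one more may be missed (35/46 = 76.1%; 34/46 = 73.9%). Without AE and EMR, one (30/39 = 76.9%; 29/39 = 74.4%). With Table 7.1 measures, two (27/35 = 77.1%; 26/35 = 74.3%). The participant must otherwise be almost complete.

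**Cohort bound.** On a measure-level count, all 24 participants needed for the goal could in principle lack post-dose data. This is an upper bound, not a forecast.

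**Reliability of the counts.** Table 7.3 was read from extracted text, but Table 7.1 gives the same verdicts. The two tables differ on objective cognition at M1 (absent in 7.1, marked in 7.3). Adding one measure at M1 to Table 7.1 gives 30/36 = 83.3% and does not change the result.

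**The case against.** The strongest reply is that use is ad libitum, staff give no dosing or frequency instructions, and so there is no regimen to adhere to. As regards dose this stands. It does not answer whether any exposure occurred or whether the post-dose tests followed an intake, and both can be counted without prescribing anything.

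Second, the plan is not blind to these events. Tb1 and Tc1 tests are study assessments and so enter the synopsis count. Section 5.4.1 promises to track participants who do not follow instructions, section 10.1 looks for measures consistently left blank, and use is recorded by photo and timeline follow-back. Section 4.2.1 also refers to a figure that is not in the available text. It would be wrong to infer that the study collects nothing on use. What stands against the plan is narrower: none of this is tied to the compliance rule. A non-user who follows the freedom to use as they see fit need not be flagged under section 5.4.1 either.

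Third, route 2 is narrow. It leaves room for only one or two further missed measures, and entrants have already decided to try cannabis. This is fair, and the documents give no basis for estimating how many participants would follow either route.

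Fourth, the phrase about all necessary components comes from the background, while the objective speaks of reasonable compliance with study procedures. But purchase, photo and the intake at the two-week appointment are themselves described as study procedures.

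**Conclusion.** The point holds in this form: the rule requires no purchase, photo or use, so a participant who never takes an oral product can be compliant. By completing every form without an intake, such a participant reaches 100%, provided the post-dose forms are administered anyway. By missing Tb1 and Tc1 only, the participant reaches 78% to 83% on cells, instruments or measures, but 60% by time points and 67% by sessions. The second route therefore depends on a unit that section 10.3.1 does not define.

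A reader might infer that someone who skips the whole acute session also passes. The documents do not support this. Sections 4.1 and 7.3.3 define that session as Ta1 to Tc1, and missing all of it leaves 40% to 67% on every count in the table, and 42.3% by minutes. Nor does the material show that the 80% result would in fact be wrong. It shows that the rule as written could not tell. The matter should be corrected, but it does not undermine the design.

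**What to change.** In section 10.3.1:

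- State the unit and denominator of study assessments, for example each scheduled measure at each time point, over all enrolled participants.
- Replace the adherence sentence with a statement that no dosing adherence is assessed, but that these proportions of all enrolled will be reported: product purchased; identifying photo received; any use of that product between T00 and Ta1; and Ta1, Tb1 and Tc1 completed around an intake.
- Report the 80% goal for participants who reach 75% and also complete Ta1–Tc1 around an intake, with the assessment-only figure beside it.
- Correct the pointer in section 3, which sends the reader to a section 10.5.4 that does not appear in the text.

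The cost is wording and tabulation, since the photo, timeline follow-back and session records are already planned. Two details need care. The follow-back covers 14 days while the visit window is 14 ± 4 days, so a visit at day 18 leaves 18 − 14 = 4 days uncovered, and a visit at day 10 reaches 14 − 10 = 4 days before baseline. And receipt of the photo should be tabulated as yes or no by the team member who holds the product information, so that the assessors stay blind. The main downside is that the compliance figure may be lower. The change sets no dose, frequency or regimen.

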#### 10.3.2 BASELINE DESCRIPTIVE STATISTICS

We will characterize the cohort based on demographics, disease stage, and other relevant descriptives.

### 10.4 SAMPLE SIZE

We plan to recruit 30 participants into this feasibility study, as we believe this will be adequate to determine whether the larger trial is possible and whether there are changes in study procedures that would be required before initiating a fully powered study.

## 10.5 MEASURES TO MINIMIZE BIAS

The investigators and research assistants will be blind to *Cannabis* edible product condition. A member of the study team not responsible for data collection will maintain the experimenter blind.

### 10.5.1 ENROLLMENT/ RANDOMIZATION/ MASKING PROCEDURES

Participants will be free to select the edible Cannabis product of their choice and use their product *ad libitum*. They will report on their selection via an individualized, emailed REDCap survey blinded to the study team with the exception of a member of the study team not responsible for data collection.

### 10.5.2 EVALUATION OF SUCCESS OF BLINDING

Because we do not anticipate the blinding to be maintained by participants, we will not assess the success of the blind.

### 10.5.3 BREAKING THE STUDY BLIND/PARTICIPANT CODE

Since participants are aware of which product they are taking, there are no conditions under which the blind needs to be broken.

## 11 SOURCE DOCUMENTS AND ACCESS TO SOURCE DATA/DOCUMENTS

We have taken a number of measures to ensure the confidentiality of the data and the safety of the participants. All data from the proposed study will be identified by a numerical ID code only. The information linking the numerical ID code to identifying information will be maintained separate and secure from the data themselves. At the conclusion of the final data collection session, the list linking the ID code to identifying information will be destroyed.

## 12 QUALITY ASSURANCE AND QUALITY CONTROL

The CUChange Lab has established standard operating procedures (SOPs) to ensure **quality assurance (QA)** in the design of databases for observational studies such as the proposed project. The data entry system has been well established with previous studies and relies on a strategy of centralized data capture through REDCap. Raw data is uploaded daily to REDCap either manually or through automated application programming interface (API) call. Professional research assistants review all case report forms and raw data at the conclusion of every study session or upon receipt of data from collaborators (such as cannabinoid lab results) as applicable.

**Quality control (QC)** SOPs at the CUChange Lab include quarterly data review of 10 randomly selected participant records. This will be logged (who checked the data, what parts of the data were checked if not all assessments, when the data was checked, and if there are any outlying

issues or discrepancies to follow-up on, and who will follow-up with any discrepancies and when).

The investigational team will provide direct access to all study-related sites, source data/documents, and reports for the purpose of monitoring and auditing by the DSMC audit team, and inspection by local and regulatory authorities.

